#### 9.7.3 Missing data

Where data are missing from the original medical record, the affected analyses will be conducted using only the results of those patients with data available and the number included in each analysis will be stated.

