# Endpoint to address the secondary objective

# Variables required to address the secondary objective

Secondary objective 1: To describe the safety profile of rapidly infused CT-P10 in patients with NHL or CLL in the 6 months post-index date

- Proportion of patients who experience the following safety events in the 6 months post-index date, and frequency of each per patient per month:
  - Any IRR.
  - Any grade 3 or grade 4 IRR (according to the Common Terminology Criteria for Adverse Events [CTCAE] version 4).
  - Any other AE (excluding IRR).
  - Any other grade 3 or grade 4 AE (excluding IRR).
  - o Any serious adverse event (SAE).
- Proportion of patients with AEs as the primary cause for treatment discontinuation.
- Summary distributions of event type by grade.
- Proportion of all rapid CT-P10 infusions during which IRRs were experienced.

For all AEs (temporally associated with CT-P10 treatment) during the 6 months post-index (including the index date):

- Description of AE
- IRR (Yes/No)
- Event start date
- Event end date
- Seriousness
- CTCAE v4.0 grade
- Clinician's assessment of relationship to CT-P10
- AE resulted in treatment discontinuation (Yes/No).

Secondary objective 2: To describe the clinical effectiveness of rapidly infused CT-P10 in patients with NHL or CLL in the 6 months post-index

- OS, defined as the time from the index date until death from any cause.
- Proportion of patients surviving at six months following NHL or CLL diagnosis and following the index date.
- PFS, defined as the time from the index date until the first documented evidence of disease progression or death from any cause.
- Proportion of patients surviving and free from disease progression at six months following the index date.
- Summary of best response to CT-P10

- Date of data collection.
- Patient alive at 6 months post-index (Yes / No / Not known)?
- If no, date of death (DD/MM/YYYY).
- All treatment response assessments in the post-index period (date, recorded treatment response [complete response / partial response / no response or stable disease / progressive disease], assessment based on IWCLL / Revised Response Criteria for Malignant Lymphoma / local criteria / other criteria, type(s) of

- (complete response / partial response / no response or stable disease / progressive disease).
- Proportion of patients achieving a complete or partial response.

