- Time to complete or partial response, defined as the number of days from the index date until first documentation of complete or partial response by the local investigator.
- assessments used to evaluate response).
- Date (within 6 months post-index) of last recorded hospital visit.

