#### 9.7.2 Secondary analyses

For the secondary endpoint safety analyses, rates of events per-patient-per month will be reported. Secondary clinical effectiveness endpoints will be reported separately for patients with NHL or CLL. The time-to-event clinical effectiveness endpoint analyses (OS, PFS, time to complete or partial response) and CT-P10 treatment duration will be displayed descriptively using Kaplan Meier plots from the index event until the date of the event or censoring. Patients who are known to be alive at 6 months post-index will be censored on that date for OS whereas patients who are lost to follow-up will be censored at the date they were last known to be alive (i.e. the last recorded hospital visit within the 6 months post-index). For PFS, patients will be censored on the date they were last known not to have disease progression (i.e. the date of last documented response assessment) and for time to complete or partial response, patients will be censored at the date of the last recorded known response. For treatment duration, censoring will occur at the 6 months post-index date (if CT-P10 treatment is known to be ongoing at 6 months) or the date of the last infusion (if the patient is lost to follow-up). Absolute counts and the percentages of these events occuring in each disease indication group will be reported. Survival rates for 6 months post NHL or CLL diagnosis will also be calculated. Summary data will be tabulated and also displayed graphically where appropriate.

The proportion of patients assessed as having a best response of complete response, partial response, stable disease or progressive disease within the 6 months post-index based the documented assessment of the local investigator and the proportion of patients with a complete or partial response, will be presented with 95% CI.

For the demographic, clinical, and NHL/CLL disease characteristics endpoint analyses, the study population will be described by means of summary statistics. Distributions and descriptive statistics of both central tendency (medians and means) and dispersion (standard deviation, interquartile range [IQR]) will be presented for

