quantitative variables. Categorical variables will be described with frequencies and percentages; distributions, modes, medians, IQR and range will be reported as appropriate. 95% CI will be presented for means and estimates of proportions, as appropriate. Where appropriate differences between disease groups will be evaluated using two-sample t-tests or Mann-Whitney U-tests for continuous normally and non-normally distributed variables, respectively, while the chi-squared test will be employed for nominal variables. Normality of variables will be evaluated through inspecting histograms of their distributions.

Treatment patterns for NHL or CLL in patients who receive rapid infusion of CT-P10 will be described for the entire study period. Summary statistics will be displayed for the treatment dose and duration on treatment, and for the treatment discontinuation reason.

All percentages will be reported to the nearest whole number; therefore, in reporting study results in tables, figures and associated text, percentages may not add up to 100% due to rounding.

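### Read literally, the available-data rule drops 'Not known' patients from six-month survival while the OS rule keeps them at risk, so the proportion falls at or below the Kaplan-Meier value

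*Protocol*

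**What the plan says.** Section 9.3 (secondary objective 2) lists, beside OS, this endpoint: "Proportion of patients surviving at six months following NHL or CLL diagnosis and following the index date". This point concerns only the part that runs from the index date. The variables include the item "Patient alive at 6 months post-index (Yes / No / Not known", the date of death, and "Date (within 6 months post-index) of last recorded hospital visit".

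Section 9.7.2 gives the censoring rules for the time-to-event analyses, which are shown as Kaplan-Meier plots. In the OS analysis, follow-up of confirmed survivors ends at the six-month date. The rule for the others reads: "patients who are lost to follow-up will be censored at the date they were last known to be alive". On event percentages, the same section says: "Absolute counts and the percentages of these events occuring in each disease indication group will be reported". No denominator is named there, and nothing says whether the six-month proportion is a simple fraction or is read from the curve.

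Section 9.7.3 is the general missing-data rule: "the affected analyses will be conducted using only the results of those patients with data available". The number of patients included in each analysis is to be stated. Section 9.7.4 plans no sensitivity analyses. Section 9.7 leaves detailed methods to an SAP, which is not at hand.

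**The concern.** The two rules treat the same patients differently. A patient with a recorded death is a No whenever the death occurred, and so always counts. A patient last seen alive at month 4 with no later record is Not known. Under 9.7.3 that patient leaves the proportion, and four months of observed survival go too. Under 9.7.2 the patient stays in the OS risk set until month 4. Inclusion in the proportion therefore depends partly on the outcome.

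At stake is a report that shows two different six-month survival figures for the same group, with the simple one pulled downward by the way its denominator is formed. Patients may be recruited before six months have elapsed (9.2.2) and interim analyses are planned (9.7.5), so the share without a known six-month status could be large at an interim.

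**Working it through.** **Inputs.** The protocol states no expected six-month survival, number of deaths or rate of loss, so there is no figure of its own to reproduce for this endpoint. All survival and loss rates below are assumptions. The expected group sizes, 240 NHL and 60 CLL, come from section 9.5.

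**1. Direction against Kaplan-Meier.** Let A be the patients known alive at six months, D the recorded deaths and U the Not known. The available-data proportion is A/(A + D). This equals the Kaplan-Meier product computed after deleting the U patients from the start. Deleting them leaves the deaths unchanged and makes each risk set n the same or smaller, so each factor (1 − 1/n) is the same or smaller. Hence A/(A + D) ≤ KM(6), with strict inequality whenever a death precedes the last visit of a Not known patient. In 5,000 simulated data sets there were no violations.

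**2. Example.** N = 240, with 12 recorded deaths early in the window and 24 patients lost later.
- Kaplan-Meier: (240 − 12)/240 = 228/240 = 95.0%.
- Available data: (240 − 12 − 24)/(240 − 24) = 204/216 = 94.4%.

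**3. Expected size with non-informative loss.** Let S be true six-month survival and L the probability of loss within six months in the absence of death. Both hazards are constant, and time is in units of six months. Put λ = −ln S and γ = −ln(1 − L).
- Known alive: a = S(1 − L).
- Recorded deaths: d = λ/(λ + γ) × [1 − S(1 − L)].
- Available-data proportion: a/(a + d).

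For S = 0.90 and L = 0.20: λ = 0.1054, γ = 0.2231, a = 0.720, d = 0.3207 × 0.280 = 0.0898. The proportion is 0.720/0.8098 = 88.9%.

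| True S | 5% loss | 10% loss | 20% loss | 40% loss |
|---|---|---|---|---|
| 98% | 97.95% | 97.89% | 97.76% | 97.40% |
| 95% | 94.9% | 94.7% | 94.4% | 93.6% |
| 90% | 89.8% | 89.5% | 88.9% | 87.3% |

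For S of 90-95% the gap is about 0.1-0.5 points at 5-10% loss and 0.6-1.1 points at 20% loss. If all patients form the denominator instead, the error goes the other way: 1 − d = 1 − 0.0898 = 91.0% for S = 90% and 20% loss.

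**4. Interim data.** Suppose a share f of patients has follow-up spread uniformly over 0-6 months and the rest are complete. The mean probability of a recorded death among the incomplete is 1 − (1 − S)/(−ln S). For S = 0.95 this is 1 − 0.05/0.05129 = 0.0252.
- f = 0.5: d = 0.5 × 0.0252 + 0.5 × 0.05 = 0.0376; a = 0.5 × 0.95 = 0.475; proportion = 0.475/0.5126 = 92.7%.
- f = 0.3 gives 94.0%, and f = 0.7 gives 89.7%.
- With S = 0.90 and f = 0.5, the result is 85.6%.

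**5. Direction against the truth.** In the example of step 2, let q be the share of the 24 Not known patients who in fact died by six months. True survival is (228 − 24q)/240. It equals 204/216 when q = 12/216 = 5.6%. Below that share the available-data figure is too low, and above it too high: true survival is 94.0% at q = 10% and 92.5% at q = 25%.

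**The case against.** The strongest reply is that no sentence in the protocol makes the six-month proportion a simple Yes/(Yes + No) fraction. The status item sits beside the date of death and the last-visit date, which together are the inputs to a censored analysis. The OS rule is specific to these patients and could be taken to govern, with the proportion read from the curve. The SAP may say so. That stands, and it is why the point is conditional on a literal reading. It does not remove the point: the censoring rule is attached only to the time-to-event analyses, nothing links the separate proportion to the curve, and 9.7.3 is the one missing-data rule whose wording reaches it.

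The second reply is size. Data collection is to be completed once six months have elapsed (9.1), so loss in the final analysis may be low. A gap of 0.1-0.5 points will often vanish, because "All percentages will be reported to the nearest whole number". At 90% survival the approximate 95% half-width is 1.96 × √(0.9 × 0.1/240) = 3.8 points for 240 patients and 7.6 points for 60. The requirement to state the number included would also make exclusions visible. All of this stands for the final analysis. It carries less weight at an interim, although the protocol does not say that survival will be reported then.

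The third reply is that Kaplan-Meier is not immune either. If deaths are hidden among the Not known, it is too high: in the example it gives 95.0% when true survival is 94.0%, further off than the 94.4% of the simple proportion. This also stands. But there the simple figure is nearer only because two errors offset each other.

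A reader might go further and infer that every death is kept, that living patients are dropped, and that reported survival is certainly too low. The documents do not support this. Only recorded deaths are kept, Not known patients are last known alive rather than known to be living, and the sign against the truth depends on hidden deaths. Nor is this a headline figure: it belongs to a secondary objective of a descriptive study whose primary endpoint is infusion-related reactions.

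**Conclusion.** The point holds in a limited form. On the literal text, 9.7.3 and the OS rule in 9.7.2 handle the same Not known patients differently, and a proportion formed under 9.7.3 lies at or below the Kaplan-Meier value whatever the mechanism of loss. That it also understates true survival follows only if loss is non-informative. In the worked example, a hidden-death share above about 5.6% of the Not known reverses the sign.

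The likely effect in the final analysis is small: mostly below half a point at 5-10% loss, and about 1 point at 20% loss with 90% survival. It could reach several points at an interim with much incomplete follow-up. All these sizes rest on assumed survival and loss rates. The matter is worth correcting because the remedy costs almost nothing, not because the main result is threatened.

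**What to change.** In sections 9.3 and 9.7.2, state that six-month survival after the index date is the Kaplan-Meier estimate at six months with its 95% CI, by disease group. It should use the OS censoring already set out in 9.7.2 and be exempt from 9.7.3. Show the counts of Yes, No and Not known only as a description of follow-up, so that a reader can judge how far hidden deaths could matter. If a crude percentage is also shown, name its denominator.

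The cost is a sentence or two in the protocol, repeated in the SAP. The last-visit date is already collected and the curve is already planned, so no new data are needed. The change is best made before the first interim.

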#### • **Serious adverse event (SAE):** a SAE is an AE that:

- is fatal
- o is life threatening (places the subject at immediate risk of death)
- o requires in-patient hospitalisation or prolongation of existing hospitalisation
- results in persistent or significant disability/incapacity
- o is a congenital anomaly/birth defect
- other significant medical hazard.

- **Adverse event grade:** AEs will be defined as grade 1, 2, 3, 4 or 5 according to the Common Terminology Criteria for Adverse Events v4.0 (CTCAE).
- **Overall survival (OS):** defined as the time from the index date to death from any cause.
- **Progression free survival (PFS):** defined as the time from the index date to the first documented evidence of disease progression or death from any cause. The assessment of disease progression will be based on the International Workshop on Chronic Lymphocytic Leukemia (IWCLL) criteria for CLL or the Revised Response Criteria for Malignant Lymphoma for NHL, if these criteria are used and documented locally. If different criteria are used in routine practice, disease progression will be defined as documented in the medical records.
- Complete response (CR) or partial response (PR): will be based on IWCLL criteria for CLL or the Revised Response Criteria for Malignant Lymphoma for NHL, if these criteria are used and documented locally. If different criteria are used in routine practice, response will be defined as documented in the medical records.

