#### 9.7.4 Subgroup and sensitivity analyses

Subgroup analyses may be conducted to further evaluate the safety and clinical effectiveness of CT-P10 in patients with NHL or CLL. This may include, but will not be limited to:

- Diagnosis (NHL [further stratified by FL / DLBCL] / CLL).
- Infusion time for the index event (90 minutes, 60<90 minutes, <60 minutes).
- Patients with / without prior exposure to a rituximab-containing regimen.

No sensitivity analyses are planned.

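### Applied literally, the available-data rule drops patients whose only events are ungraded from the grade 3 or 4 proportions but keeps every event-free patient, which can bias those proportions in either direction

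*Protocol*

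**What the plan says.** Protocol section 9.7.3 gives a single rule for data that the notes do not contain: "the affected analyses will be conducted using only the results of those patients with data available". It makes no exception for event grade. The one accompanying safeguard is a reporting one, that "the number included in each analysis will be stated". Section 9.7.4 adds: "No sensitivity analyses are planned".

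In section 9.3, secondary objective 1 defines its safety endpoints as "Proportion of patients who experience the following safety events in the 6 months post-index date, and frequency of each per patient per month". Two of the listed events depend on grade: "Any grade 3 or grade 4 IRR (according to the Common Terminology Criteria for Adverse Events [CTCAE] version 4") and "Any other grade 3 or grade 4 AE (excluding IRR"). The data item behind both, "CTCAE v4.0 grade", is collected once for each AE. Section 2.2 says that "AEs will be defined as grade 1, 2, 3, 4 or 5 according to the Common Terminology Criteria", but not who assigns the grade when the notes contain none.

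**The concern.** The endpoint is counted per patient, while the variable that can be missing exists only per event. A patient with no event has no grade to lose and always stays in the denominator as a non-case. A patient whose events all lack a grade has no usable value for this endpoint and, under 9.7.3, leaves the analysis. Only patients who had an event can be removed. Restricting to available data is therefore not neutral here, even if grades are missing completely at random among events.

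Missing grades are foreseeable. The source is routine hospital records reviewed retrospectively, and section 9.9 concedes that interpretation depends on how complete those records are. The limitations listed there do not mention this selective exclusion. Severe IRRs are a named secondary objective of a safety study, so their reported proportion should not depend on how often centres write down a grade.

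**Working it through.** **Inputs from the protocol (section 9.5).** Sample size 300, planning IRR rate 10%, highest IRR rate in earlier studies about 30%. The plan's own figure reproduces: an exact (Clopper-Pearson) 95% interval for 30/300 is 6.8% to 14.0%, as stated. The protocol gives no grade 3 or 4 rate and no missing-grade rate.

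**Assumptions.** Severe share among IRR patients 10%; for AEs, 80% of patients with an AE and 30% of those severe; missing-grade shares as shown below. The 10% IRR rate is a planning figure for the primary endpoint (index infusion), borrowed here to illustrate a six-month endpoint. Each event patient is treated as wholly graded or wholly ungraded.

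**Formula.** Let π be the share of patients with an event, s the severe share among them, m_s and m_n the shares of severe and non-severe event patients left ungraded, and m = s·m_s + (1−s)·m_n.

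- True proportion: π·s
- Proportion under 9.7.3: π·s·(1−m_s) / (1−π·m)

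The two agree only if m_s = π·m. The estimate is too low if m_s > π·m and too high if m_s < π·m. If grades are missing equally (m_s = m > 0), it is too low whenever π < 1.

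**IRRs: 300 patients, 30 with an IRR, 3 severe, true 3/300 = 1.0%.** Let u be the share of the 30 left ungraded.

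| u | Missing equally: 3(1−u)/(300−30u) | All ungraded are mild: 3/(300−30u) |
|---|---|---|
| 20% | 2.4/294 = 0.82% | 3/294 = 1.02% |
| 40% | 1.8/288 = 0.625% | 3/288 = 1.04% |
| 60% | 1.2/282 = 0.43% | 3/282 = 1.06% |

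At the 30% IRR rate (90 IRR patients, 9 severe, true 3.00%), with 30% of grades missing equally: 6.3/273 = 2.31%. With 30% of only the non-severe grades missing: 9/275.7 = 3.26%.

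**Other AEs: 300 patients, 240 with an AE, 72 severe, true 72/300 = 24.0%.**

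- 30% of grades missing equally: 50.4 graded severe, 72 patients dropped, 50.4/228 = 22.1%.
- 30% of only the non-severe grades missing: 0.3 × 168 = 50.4 patients dropped, 72/249.6 = 28.8%.

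**Full denominator with bounds (equal missingness).** The first figure counts ungraded patients as not severe, the second as severe.

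- IRRs, u = 20%: 2.4/300 = 0.80% and 8.4/300 = 2.8%
- IRRs, u = 40%: 1.8/300 = 0.60% and 13.8/300 = 4.6%
- IRRs, u = 60%: 1.2/300 = 0.40% and 19.2/300 = 6.4%
- AEs, 30% missing: 50.4/300 = 16.8% and 122.4/300 = 40.8%

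Each pair contains the true value. The lower bound alone is no better than the present rule under equal missingness (0.80% against 0.82%).

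**The case against.** Five points can be made for the plan.

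*Grades may rarely be missing.* Section 2.2 treats grade as something the study defines. Section 9.8 provides guidelines, training, completeness checks and a pilot, and section 9.6 has the investigator resolve queries against source records. On that reading, a record describing a hospital admission but no written grade need not count as missing. This stands as mitigation, but none of these provisions says how a grade is assigned or what happens to events that stay ungraded.

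*Severe events are also captured without grade.* The serious-AE endpoint includes hospitalised and life-threatening events. That is a fair partial cross-check, though seriousness and grade 3 or 4 are different endpoints.

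*The IRR shifts are slight.* Section 9.7.2 rounds percentages to whole numbers, so all the IRR results at the 10% rate print as 1% except 0.43%, which prints as 0%. The exact 95% interval for 3/300, 0.2% to 2.9%, is wider than every one of those shifts. This stands for IRRs. It does not cover AEs, where the illustrative shifts reach about 5 percentage points.

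*Keeping everyone in the denominator does not by itself remove bias.* Correct, as the lower bounds show. The gain comes from recovering grades and showing both bounds.

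*This belongs in the SAP.* Detailed methods are deferred there, but the protocol already fixes the rule and plans no sensitivity analyses. Stating the number analysed discloses the exclusion without correcting it.

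A reader might also infer that the severe-event proportion must fall as documentation worsens. The documents do not support that. Section 9.9 expects under-recording particularly of milder events; if grading followed the same pattern, the proportion would tend to rise.

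**Conclusion.** The point holds as a misfit between a stated rule and two secondary endpoints. Read literally, section 9.7.3 makes exclusion from the grade 3 or 4 proportions conditional on having had an event. The direction of the bias is not fixed, and its size cannot be known from the protocol.

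Under the stated assumptions it is small in absolute terms for IRRs and possibly larger for AEs, and it disappears if every event is graded. The missing-grade shares, the severe shares and the 80% AE rate are all assumptions. The rule also leaves open how to treat a patient who has one graded severe event and another ungraded one.

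A reader might infer that the main safety result is compromised. It is not: the primary endpoint, any IRR over six months and serious AEs can all be determined without a grade. The change is worthwhile because it is cheap, not because the study's main conclusion is at risk.

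**What to change.** Exempt event grade from section 9.7.3 and state the following instead:

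- Data collectors assign the CTCAE v4.0 grade from the documented facts under the data collection guidelines, with a query to the investigator where the facts are unclear.
- All patients stay in the denominator. A patient with any event graded 3 or 4 counts as a case, whatever else is ungraded.
- Events that remain ungraded are shown as their own category.
- The grade 3 or 4 proportion is reported as a range, with ungraded events counted first as not severe and then as severe.

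The cost is a short change to 9.7.3, one item in the guidelines and two extra table rows. The downside is that some grades will rest on abstraction rather than on the treating team's own entry, and the bounds may be wide if many grades are missing.
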